# 8.6 Audits and inspections

Authorised representatives of AstraZeneca, a regulatory authority, or an Ethics Committee may perform audits or inspections at the centre, including source data verification. The purpose of an audit or inspection is to systematically and independently examine all studyrelated activities and documents, to determine whether these activities were conducted, and data were recorded, analysed, and accurately reported according to the protocol, Good Clinical Practice (GCP), guidelines of the International Conference on Harmonisation (ICH), and any applicable regulatory requirements. The investigator will contact AstraZeneca immediately if contacted by a regulatory agency about an inspection at the centre.

# 9. STUDY MANAGEMENT BY ASTRAZENECA

# 9.1 **Pre-study activities**

Before the first subject is entered into the study, it is necessary for a representative of AstraZeneca to visit the investigational study site to:

- Determine the adequacy of the facilities
- Determine availability of appropriate subjects for the study
- Discuss with the investigator(s) (and other personnel involved with the study) their responsibilities with regard to protocol adherence, and the responsibilities of AstraZeneca or its representatives. This will be documented in a Clinical Study Agreement between AstraZeneca and the investigator.

# 9.2 Training of study site personnel

Before the first subject is entered into the study, an AstraZeneca representative will review and discuss the requirements of the Clinical Study Protocol and related documents with the investigational staff and also train them in any study specific procedures and the WBDC system(s) utilised.

The Principal Investigator will ensure that appropriate training relevant to the study is given to all of these staff, and that any new information relevant to the performance of this study is forwarded to the staff involved.

The Principal Investigator will maintain a record of all individuals involved in the study (medical, nursing and other staff).

# 9.3 Monitoring of the study

During the study, an AstraZeneca representative will have regular contacts with the study site, including visits to:

• Provide information and support to the investigator(s)

- Confirm that facilities remain acceptable
- Confirm that the investigational team is adhering to the protocol, that data are being accurately and timely recorded in the CRFs, that biological samples are handled in accordance with the Laboratory Manual and that study drug accountability checks are being performed
- Perform source data verification (a comparison of the data in the CRFs with the subject's medical records at the hospital or practice, and other records relevant to the study) including verification of informed consent of participating subjects. This will require direct access to all original records for each subject (eg, clinic charts)
- Ensure withdrawal of informed consent to the use of the subject's biological samples is reported and biological samples are identified and disposed of/destroyed accordingly, and the action is documented, and reported to the subject.

The AstraZeneca representative will be available between visits if the investigator(s) or other staff at the centre needs information and advice about the study conduct.

# 9.3.1 Source data

Refer to the Clinical Study Agreement for location of source data.

# 9.4 Study agreements

The Investigator at each/the centre should comply with all the terms, conditions, and obligations of the Clinical Study Agreement, or equivalent, for this study. In the event of any inconsistency between this Clinical Study Protocol and the Clinical Study Agreement, the terms of Clinical Study Protocol shall prevail with respect to the conduct of the study and the treatment of subjects and in all other respects, not relating to study conduct or treatment of subjects, the terms of the Clinical Study Agreement shall prevail.

Agreements between AstraZeneca and the Principal Investigator should be in place before any study-related procedures can take place, or subjects are enrolled.

# 9.4.1 Archiving of study documents

The Investigator follows the principles outlined in the Clinical Study Agreement (CSA).

# 9.5 Study timetable and end of study

The end of the study is defined as 'the last visit of the last subject undergoing the study'.

The study is expected to start in Q2 2013 and to end by Q4 2015.

The study may be terminated at individual centres if the study procedures are not being performed according to GCP, or if recruitment is slow. AstraZeneca may also terminate the

entire study prematurely if concerns for safety arise within this study or in any other study with ticagrelor.

# 10. DATA MANAGEMENT BY ASTRAZENECA

Data management will be performed by AstraZeneca Selected CRO which will be responsible for all the Data Management activities.

The data collected through third party sources will be obtained and reconciled against study data.

Adverse events and medical/surgical history will be classified according to the terminology of the latest version the Medical Dictionary for Regulatory Activities (MedDRA). Medications will be classified according to WHO Drug Dictionary. All coding will be performed by Astrazeneca selected CRO which will be responsible for all the Data Management activities.

Data queries will be raised for inconsistent, impossible or missing data. All entries to the study database will be available in an audit trail.

The data will be validated as defined in the Data Management Plan. Quality control procedures will be applied to each stage of data handling to ensure that all data are reliable and have been processed correctly.

When all data have been coded, validated, signed and locked, clean file will be declared.

# 11. EVALUATION AND CALCULATION OF VARIABLES BY ASTRAZENECA

# **11.1** Calculation or derivation of efficacy variable(s)

Efficacy assessment will describe the incidence of major CV events (composite of CV death, MI, stroke), analyzed according to locally adjudicated PLATO definitions.

# **11.2** Calculation or derivation of safety variable(s)

The safety assessment will describe total major bleeding events (including the subsets of fatal and fatal/ life threatening events), combined major and minor bleeding events and major/minor/minimal bleeding events. Bleeding events will be analyzed according to locally adjudicated PLATO bleeding definitions. AEs and other SAEs other than bleeding will also be evaluated. Summaries will be presented using descriptive statistics.

- Primary variables
  - PLATO-defined fatal/life-threatening bleedings during 1 year follow up in Chinese ACS patients treated with ticagrelor.

- PLATO-defined major bleedings during 1year follow up in Chinese ACS patients treated with ticagrelor.
- PLATO-defined major + minor bleedings during 1 year follow up in Chinese ACS patients treated with ticagrelor.
- PLATO-defined major + minor + minimal bleedings during 1 year follow up in Chinese ACS patients treated with ticagrelor.
- Serious adverse events other than bleeding during 1 year follow up in Chinese ACS patients treated with ticagrelor.
- Other variable

Major CV events during 1 year follow up in Chinese ACS patients treated with ticagrelor.

### 11.2.1 Other significant adverse events (OAE)

During the evaluation of the AE data, an AstraZeneca medically qualified expert will review the list of AEs that were not reported as SAEs and DAEs. Based on the expert's judgement, significant adverse events of particular clinical importance may, after consultation with the Global Patient Safety Physician, be considered OAEs and reported as such in the Clinical Study Report. A similar review of laboratory/vital signs data will be performed for identification of OAEs.

Examples of these are marked haematological and other laboratory abnormalities, and certain events that lead to intervention (other than those already classified as serious), dose reduction or significant additional treatment.

- **11.3** Calculation or derivation of patient reported outcome variables (Not applicable)
- **11.4** Calculation or derivation of pharmacokinetic variables (Not applicable)
- 11.5 Calculation or derivation of pharmacodynamic variable(s) (Not applicable)
- **11.6** Calculation or derivation of pharmacogenetic variables (Not applicable)
- 11.7 Calculation or derivation of health economic variables (Not applicable)

# 12. STATISTICAL METHODS AND SAMPLE SIZE DETERMINATION BY ASTRAZENECA

# 12.1 Description of analysis sets

All subjects who received at least one dose of investigational product, and for whom any postdose data are available will be included in the safety population.

Patients will be censored at 7 days after their last dose of ticagrelor. Patients who withdraw consent to participate in the study will be included up to the date of their study termination. Primary analyses of all safety variables will use the safety analysis set.

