### Efficacy and bleeding in the overall PLATO cohort, Asia and China

KM: Kaplan-Meier, MI: myocardial infarction, CV: cardiovascular

Efficacy analyses performed on Full analysis set, safety analyses on Safety analysis set

The HR for the comparison of ticagrelor to clopidogrel for the primary composite endpoint of CV death, MI, and stroke (HR 0.77 [95% CI 0.42, 1.43]; p=0.4086) was not statistically significant in the China cohort alone. This result is generally consistent with PLATO overall, which shows superior efficacy observed for ticagrelor.

In safety analyses, the Chinese cohort had a much smaller sample size and a corresponding wider CII (HR 1.72 [95% CI 0.72, 4.09]; p=0.2225). There were numerically more 'Total Major' bleeding events in the ticagrelor group (n=14) compared to clopidogrel (n=8), but the difference was not statistically significant. It is concluded that this result is consistent with PLATO overall, and that 'Total Major' bleeding in the China cohort did not differ between the treatment groups.

On November 22nd 2012, ticagrelor was approved by State Food and Drug Administration (SFDA); AstraZeneca (AZ) was required by SFDA to conduct a post-approval study to describe the safety profile of ticagrelor in Chinese ACS patients.

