# 5.2.1 **Procedures for randomisation (Not applicable)**

# 5.3 **Procedures for handling subjects incorrectly enrolled**

**Subjects who fail to meet the inclusion/exclusion criteria** should not, under any circumstances, be enrolled. There can be no exceptions to this rule.

If a patient does not meet the selection criteria but is enrolled in error, a discussion should occur between the Study Physician and the Investigator regarding whether to continue or discontinue the patient from study medication. Consistent with Intent-To-Treat (ITT) principles, all enrolled patients should continue to be followed in the study (ie, attend protocol visits) and, unless treatment would be harmful, patients should continue to receive study medication.

In situations where an agreement cannot be reached, the patient should have their study medication stopped but will continue with study assessments. The Study Physician is to ensure all such decisions are appropriately documented.

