### 5.8.3 **Permanent premature discontinuation from study medication**

Patients permanently discontinuing study medication should be given conventional therapy, if applicable. This medication(s) will be open label and obtained locally. All patients should always be asked to continue the regular visits as described below. It is essential to collect as much data as possible for all patients throughout the study. Complete withdrawal from the study (withdrawal of consent) has a direct impact on the potential validity of all study data and should be avoided wherever possible.

If the patient prematurely permanently discontinues study medication, there could be several different options for their continuation in the study as described below.

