# 5.9 Withdrawal from study

Subjects are at any time free to withdraw from study (investigational product and assessments), without prejudice to further treatment (withdrawal of consent). Such subjects will always be asked about the reason(s). If possible, they will be seen and assessed by an investigator; final visits should be 1 weeks after the discontinuation (See table 2). Adverse events will be followed up by the investigator for as long as medically indicated, but without further recording in the case report form ); and all study drugs should be returned by the subject.

The Investigator should always ask the patient to allow contact 12 months after enrolment for a final follow-up to ascertain clinical endpoints and AEs even if participation in other visits is not agreed. At a minimum, permission to ascertain vital status should be obtained if at all possible. This agreement should be noted and signed by both the Investigator and the patient on the Informed consent form, as well as entered in the medical records. The reason for discontinuation and the date of discontinuation from the study must be documented in the CRF.

Withdrawn subjects will not be replaced.

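### Section 12.1 censors at last dose plus 7 days without naming the variables covered; read literally, major CV events after stopping are collected to 12 months but left out of the 1-year figure

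*Protocol*

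**What the plan says.** Section 12.1 defines one population, the safety population: patients with at least one dose and any post-dose data. Three sentences follow that definition:

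- The first sets the cut-off: "Patients will be censored at 7 days after their last dose of ticagrelor".
- The second gives consent withdrawal its own rule: those patients contribute data until they leave the study.
- The third assigns the analysis set: "Primary analyses of all safety variables will use the safety analysis set".

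Only the third names the variables it applies to. No set or event window is given for efficacy.

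The endpoint at issue appears in section 11.2 as "Major CV events during 1 year follow up in Chinese ACS patients treated with ticagrelor". It is listed there as the other variable, under the heading for safety variables. Section 2.2 makes its 1-year incidence a secondary objective.

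On follow-up after stopping drug, section 5.8.3 says "It is essential to collect as much data as possible for all patients throughout the study". Section 5.8.3.1 prefers in-person visits to 12 months. Section 5.8.3.2 offers telephone or other contact through Visit 6, to find out about endpoints. For patients who leave the study, section 5.9 adds: "The Investigator should always ask the patient to allow contact 12 months after enrolment for a final follow-up to ascertain clinical endpoints and AEs".

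Section 12.2 plans frequencies and percentages for categorical data and names no time-to-event estimate.

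**The concern.** The follow-up sections and the analysis section serve different quantities. Following everyone to 12 months supports a 1-year incidence in patients who started ticagrelor. Cutting each patient at last dose plus 7 days supports an on-treatment count. Both are legitimate descriptions, but only the first is what the secondary objective names.

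Under the literal rule, a CV death, MI or stroke on day 8 or later after the last dose is ascertained and then dropped. It need not surface elsewhere in the report, because section 6.4.4.1 keeps these events out of AE and SAE reporting. With a crude percentage over a fixed denominator, dropping events can only lower the figure.

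The two inclusion sentences in section 12.1 also collide. Take a patient who stops drug at month 2 and withdraws consent at month 8. One sentence ends the data at month 2 plus 7 days, the other at month 8. On the second reading, a patient who withdraws could be counted for longer than one who stops drug and stays in follow-up.

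**Working it through.** **The plan's own figure.** The only numerical target is in section 12.3: a 5.7% fatal/life-threatening bleeding rate, 2000 patients, precision ±1%. Half-width = 1.96 × √(0.057 × 0.943 / 2000) = 1.02 points, which agrees after rounding. The censoring rule does not enter it. The same formula at 8.7% gives 1.96 × √(0.087 × 0.913 / 2000) = 1.24 points, a yardstick for what follows.

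**Inputs.**
- From the protocol: 2000 patients; 8.7% 12-month Kaplan–Meier rate of CV death/MI/stroke on ticagrelor in the China cohort (Table 1, 18 events in 209 patients); 7-day window.
- Assumed, because the protocol gives no figures: a proportion D of 10–30% stops by 12 months, half of them spread evenly over the first 3 months and half over months 3–12; constant event hazard on drug; hazard unchanged or doubled after the 7-day window; complete follow-up.

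**Step 1, hazard.** λ = −ln(1 − 0.087) = 0.0910 per year.

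**Step 2, counted risk in a patient who stops.** The cut-off is at c = stop time + 7/365 year. Mean c is 0.125 + 0.019 = 0.144 for early stoppers and 0.625 + 0.019 = 0.644 for late ones. Using these means, 1 − exp(−λc) is 1.30% and 5.69%, on average 3.50%.

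**Step 3, full 12-month risk in the same patient.**
- Risk unchanged: 8.70%.
- Risk doubled after c: 1 − exp(−λ(2 − c)) is 15.54% (early) and 11.61% (late), on average 13.58%.

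**Step 4, shortfall in the crude percentage.** Patients who do not stop contribute the same to both counts, so the shortfall is D × (full − counted):
- unchanged: D × (8.70 − 3.50) = D × 5.20 points
- doubled: D × (13.58 − 3.50) = D × 10.08 points

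| Stopping | Counted | Full, risk unchanged | Shortfall (events of 2000) | Full, risk doubled | Shortfall (events of 2000) |
|---|---|---|---|---|---|
| 10% | 8.2% | 8.7% | 0.5 (10) | 9.2% | 1.0 (20) |
| 20% | 7.7% | 8.7% | 1.0 (21) | 9.7% | 2.0 (40) |
| 30% | 7.1% | 8.7% | 1.6 (31) | 10.2% | 3.0 (60) |

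**Step 5, sensitivity to timing.** A day-by-day model with stopping at a constant rate over the year gives:
- Constant event hazard: shortfall 0.4–1.3 points if risk is unchanged, 0.8–2.5 if it doubles.
- Half of the event hazard in the first 30 days: 0.2–0.7 points if risk is unchanged, 0.5–1.4 if it doubles (5 to 29 events).

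Front-loading shrinks the loss because more events occur before patients stop.

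**Step 6, Kaplan–Meier with the same censoring.** In these models the estimate stays at 8.7%. If risk is unchanged, that is the true value and there is no bias. If risk doubles, the shortfall is D × (13.58 − 8.70) = D × 4.88, or 0.5 to 1.5 points for 10–30% stopping.

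**The case against.** The strongest reply is about scope. The censoring sentence stands between the definition of the safety population and the statement on safety variables, so it may have been meant for safety alone. The efficacy set may be in a statistical analysis plan that is not shown. This stands as a possible reading of intent. It does not remove the point: the sentence carries no limit, section 11.2 lists major CV events under the safety heading, and on the narrower reading the efficacy variable has no stated cut-off. One clarification settles both cases.

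A second reply is that an on-treatment count suits patients treated with ticagrelor, and that the bleeding and SAE variables carry the same 1-year wording. Both are true. The count is legitimate if labelled as such, and the scope of the rule needs stating for those variables too.

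Several stronger readings are tempting but unsupported:

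- That this is the only rule. Consent withdrawal has its own sentence.
- That the protocol commits to ITT analysis. ITT principles appear only in section 5.3, on patients enrolled in error ("all enrolled patients should continue to be followed in the study (ie, attend protocol visits"), and concern follow-up. Section 5.8.3 does not mention them.
- That Table 1 binds this trial. Its footnote, "Efficacy analyses performed on Full analysis set, safety analyses on Safety analysis set", describes PLATO, and section 3.2 rules out comparison with those outcome data.
- That the figure would describe only patients who tolerated the drug. Patients who stop still contribute events up to last dose plus 7 days.
- That understatement is certain. It follows for a crude percentage, but for Kaplan–Meier only if risk rises after stopping, on which the protocol gives no figure.

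**Conclusion.** The point holds as a conflict between an unscoped analysis rule and the stated endpoint and follow-up. Followed as written with crude percentages, section 12.1 yields an on-treatment count below the 1-year incidence of major CV events. The direction for the crude percentage does not depend on the assumptions, provided some events occur after the window; the size does. With 10–30% stopping, half of it in the first 3 months, and a constant hazard from 8.7%, the shortfall is about 0.5–1.6 points at unchanged risk and up to about 3 points at doubled risk. It is smaller if events cluster early. The upper part of that range exceeds the 1.24-point half-width of the confidence interval. The 8.7% base is itself imprecise, resting on 18 events.

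Severity is should-fix. The variable is secondary and descriptive in a single-arm study, the planned precision for bleeding is untouched, and the planned follow-up would allow either count to be produced.

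**What to change.** In section 12.1:

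1. State which variables the last-dose plus 7 days cut-off covers.
2. Reconcile that cut-off with the consent-withdrawal sentence, so that one rule applies to a patient who stops drug and later withdraws, and say how a consented 12-month contact under section 5.9 is used.
3. For major CV events, name the set (all patients with at least one dose) and count events to 12 months regardless of discontinuation, including telephone contacts and the consented 12-month contact.
4. Present the last-dose plus 7 days count as supportive, labelled as on-treatment.

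The cost is one paragraph and one extra table, from data the protocol already plans to collect. The reported event rate will probably look slightly less favourable.

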### 5.8.2 Temporary discontinuation from study medication

- Surgery or procedures associated with major haemorrhage: It is recommended that cardiac surgery and major non-cardiac surgery that in the opinion of the investigator poses a risk for clinically major bleeding not be performed until at least 7 days after stopping study medication to avoid excessive bleeding. After surgery, study medications should be restarted when the risk of bleeding is deemed low in the judgment of the investigator.
- Major bleeding: Study medication must be stopped immediately in case of a bleed deemed to be clinically significant in the judgment of the investigator (eg, a significant fall in haemoglobin, need for transfusion, haemodynamically significant, or in a critical location such as intracranial, intraspinal, intraocular, or pericardial), but may be reinstated when the risk of bleeding is deemed low in the judgment of the Investigator and if not contraindicated. The study medication administration need not be stopped in case of a minor bleeding. All bleedings should be treated and followed up according to local clinical practice. Major bleeding events should be managed according to need with general support and blood.
- Study medication should be restarted at the investigator's discretion to minimise the risk of thrombotic complications
- Dypnea: Evaluation of a patient who develops dyspnea should start with an assessment of timing relative to initiation of study drug, severity, and the presence of any signs or symptoms suggestive of cardiopulmonary disease. In patients with signs and symptoms suggestive of another cause of dyspnea (eg, heart failure exacerbation, chronic obstructive pulmonary disease flare), evaluation and treatment for those conditions should occur per local practice standards.

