### 6.4.3 Recording of adverse events

### Time period for collection of adverse events

AEs/SAEs will be recorded from the time of informed consent to last contact

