# 12.2 Methods of statistical analyses

Statistical methods will be descriptive. For continuous data, descriptive statistics will be presented as number of patients (n), mean, standard deviation (SD), median, minimum and maximum. For categorical data, the frequency and percentage of patients in each category will be presented. Counts that are zero will be displayed as "0". Percentages will be based on non-missing data unless otherwise specified.

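### The 7-day censoring rule has no clause for interruptions, so a bleed more than 7 days after stopping counts only if the patient later restarts

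*Protocol*

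**What the plan says.** Section 12.1 sets a single cut-off: "Patients will be censored at 7 days after their last dose of ticagrelor". It adds that "Primary analyses of all safety variables will use the safety analysis set", so the cut-off governs the primary bleeding variables. It has no separate rule for patients who stop and restart.

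Section 5.8.2 expects such patients. For cardiac surgery, and for major non-cardiac surgery with a risk of major bleeding, it recommends that the operation "not be performed until at least 7 days after stopping study medication to avoid excessive bleeding". It continues: "After surgery, study medications should be restarted when the risk of bleeding is deemed low in the judgment of the investigator". Amendment 1 alters only the dyspnoea text of that section and leaves 12.1 alone.

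Section 11.2 words the leading primary variable as "PLATO-defined fatal/life-threatening bleedings during 1 year follow up in Chinese ACS patients treated with ticagrelor". Section 6.4.3 states that "AEs/SAEs will be recorded from the time of informed consent to last contact", and section 6.4.9.1 requires bleed-specific CRF information for every bleeding event. Bleeds during an interruption are therefore collected. Only the analysis rule can remove them.

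**The concern.** In its plain sense a patient's last dose is the final one, and this is known only in retrospect. While a patient is off drug, nobody can say whether the dose already taken was the last. That is settled by whether treatment resumes, and under 5.8.2 resumption depends on how the investigator judges bleeding risk, which a post-operative bleed will influence.

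Two patients with the same exposure and the same bleed date can therefore be treated differently because of what happens afterwards. The one who recovers and restarts keeps the event in the analysis. The one who dies of the bleed, or is never restarted, is censored before it. The events at risk of being dropped are selectively the worse ones, in a regulatory-commitment safety study sized on fatal/life-threatening bleeding (section 12.3). An operation timed as 5.8.2 recommends falls at or beyond the end of the 7-day window, so the protocol itself creates the circumstance in which the rule misbehaves.

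**Working it through.** **1. The plan's own figure.** Section 12.3 gives p = 5.7%, n = 2000, and precision of about 1 point with a 95% CI.
- Half-width = 1.96 × √(0.057 × 0.943 / 2000) = 0.01016, or 1.016 points. The stated precision is reproduced after rounding.
- Expected events = 2000 × 0.057 = 114.

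**2. What the rule does.** Take a patient who stops on day 100. Read literally, a bleed counts if its day is no later than the final dose day + 7. The cut-off is day 107 with no restart. It is day 372 if the patient restarts and takes the final dose on day 365.

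| Bleed day | Literal rule, never restarts | Literal rule, restarts | Window from most recent dose before the bleed (either patient) | All 1-year follow-up (either patient) |
|---|---|---|---|---|
| 103 | counted | counted | counted | counted |
| 107 | counted | counted | counted | counted |
| 108 | dropped | counted | not counted | counted |
| 110 | dropped | counted | not counted | counted |
| 120 | dropped | counted | not counted | counted |

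The literal rule is the only one whose answer changes with later restart. A fatal bleed beyond day 107 is always dropped, since no restart is possible. Because 12.2 provides that "For categorical data, the frequency and percentage of patients in each category will be presented", each patient dropped in this way comes straight off the reported percentage.

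**3. Size, built up from surgery.** All three inputs are assumptions, as the documents give none of them:
- 1% to 3% of 2000 patients have surgery during such an interruption: 20 to 60 patients.
- 20% to 40% of these have a bleed that meets a fatal/life-threatening criterion beyond the window.
- 10% to 30% of those never restart.

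Low end: 20 × 0.2 × 0.1 = 0.4 events. High end: 60 × 0.4 × 0.3 = 7.2 events, and 7.2 / 2000 = 0.36 points.

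**4. Size, as a share of the 114 expected events.** Let s be the share of fatal/life-threatening bleeds that fall more than 7 days into an interruption, and q the share of those patients who never restart. Both are assumed. Events lost = 114 × s × q, and the reported rate = 5.70% × (1 − s × q).
- s = 2%, q = 25%: 0.6 lost, reported 5.67%.
- s = 10%, q = 50%: 5.7 lost, reported 5.42%.
- s = 20%, q = 100%: 22.8 lost, reported 4.56%.

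The loss reaches 1 point only if s × q is at least 0.01 / 0.057 = 17.5%. Within this deliberately wide range only the extreme corner does so.

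**The case against.** The best argument against the point is that the protocol speaks of the last dose, not the last dose ever. The text does not exclude the last dose before the event, and how interruptions enter an on-treatment window is often left to the SAP. This stands in part, since the ambiguity is real. But the protocol has not left the cut-off open. It fixes one, and its natural reading makes inclusion depend on the outcome. An SAP that follows it inherits the problem.

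A second argument is that anchoring the window to the most recent dose does not bring back the fatal post-operative bleed. This is correct. As the table shows, anchoring treats the two patients alike by excluding both. Judged against an on-treatment definition, the literal rule loses nothing and over-counts bleeds in restarters. The loss exists only against the 1-year follow-up in the variables' wording, so the anchored window alone is not a sufficient repair.

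A reader might also infer more than the documents support:
- *That fatal and severe bleeds are dropped in general.* They are not. A bleed on drug or within 7 days of stopping counts whatever follows, including death.
- *That the major-bleeding text of 5.8.2 shows the same fault.* There the bleed comes first and causes the stop, so that bleed is counted under either reading. Only the surgery text shows the mechanism.
- *That a sizeable fraction of fatal bleeds would vanish.* Table 1's fatal-bleed rates of 0.3% to 0.5% imply 6 to 10 in 2000 patients, but nothing shows how many fall in an interruption. Applied to 20 to 60 surgical patients, those rates give 0.06 to 0.3. Surgical risk may be higher, but no figure is available.
- *That most planned-surgery bleeds fall in the gap.* The documents give neither the frequency of surgery nor the timing of post-operative bleeds, and exclusion 8 keeps out patients with urgent CABG planned within 7 days of enrolment.

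**Conclusion.** The point holds in a limited form. Section 12.1 read with the surgery text of 5.8.2 makes the inclusion of a bleed more than 7 days into an interruption depend on later restart, and hence on how the bleed turned out. This follows from the wording and needs no assumption beyond the plain reading of the last dose.

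The size does rest on assumptions. With the surgical inputs of step 3 it is 0.4 to 7.2 events, at most 0.36 points on 5.7%, about a third of the 1.016-point half-width. It would rival the planned precision only under the extreme inputs of step 4. For fatal/life-threatening bleeding measured over the 1-year follow-up, its direction is fixed: the literal rule can only lower the figure. A reader might take this as a challenge to the sample size or to the study's overall conclusions, but the arithmetic does not support that. It is a small, one-directional flaw in a primary safety definition, worth correcting before analysis because the correction is simple.

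**What to change.** Make two changes in section 12.1, carried into the SAP:

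1. Define an on-treatment event as one occurring no later than 7 days after the most recent dose taken before the event, whether or not ticagrelor is later resumed. This removes the dependence on restart.
2. Beside it, report the number and percentage of patients with each primary bleeding variable (fatal/life-threatening, major, major + minor, major + minor + minimal) over all of the 1-year follow-up, regardless of dosing. This recovers the dropped events and matches the wording of section 11.2.

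With frequencies and percentages as the stated summary, no adjustment of time at risk is needed. It would matter only if a time-based rate were reported.

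The cost is a revised definition and one extra table. Stop and restart dates are needed, and section 5.7 already requires drug administration to be recorded in the CRF. Events are already recorded to last contact. A few off-drug bleeds in restarters will leave the on-treatment count, but they remain in the all-follow-up count. The change is analytic only: no visit, dose, stopping or restart rule is affected.
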